## APPENDIX 1. PROGRAMMING CONVENTIONS FOR OUTPUTS

### OUTPUT CONVENTIONS

#### TABLE AND LISTING OUTPUT CONVENTIONS

##### General:

- The first row in the body of the table or listing should be blank.
- The left-hand column should start in column 1. No indenting or centering of the output should occur.
- Rounding should be done with the SAS function ROUND, if no further specification.
- Numbers in tables should be rounded, not truncated, if no further specification.
- Alphanumeric output should be left aligned.
- Numbers should be decimal point aligned.
- Whole numbers should be right aligned.
- Text values should be left aligned.
- The first letter of a text entry should be capitalized.
- Listings of adverse events, concomitant medications, medical histories etc. should be sorted in chronological order, with earliest adverse event, medication or history coming first.
- The trial drug should appear first in tables with treatments as columns.
- In general, only present totals (across treatment groups) at baseline/randomization, and do not present them post randomization.
- If possible, include 100% frequencies in the table shell, so that it is clear what the denominator is for percentage calculations.
- All listing outputs should be sorted (preferably by Treatment, Site Number and Subject Number).
- Do not use superscripts and subscripts.
- The width of the entire output should match the linesize.

##### Univariate Statistics:

- Statistics should be presented in the same order across tables (i.e., n, Mean, SD, Median, IQR, Minimum, Maximum or n, gMean, gCV, Mean, CV, SD, Median, Minimum, P10, Q1, Q3, P90 Maximum)
- Table statistics should line up under the N part of the (N=XXX) in the table header. All decimal points should line up. If the minimum and maximum are output on one line as Minimum, Maximum then the comma should line up with the decimal point.
- If the original data has N decimal places, then the summary statistics should have the following decimal places:
  - Minimum and maximum: N
  - Mean, gMean, median, gCV% and CV%: N + 1

Document: BI\_1297-0015\_SAP\_Final\_v1.0

Author: [REDACTED]

Version Number:

Final 1.0

Version Date:

30Sep2022

Template No: CS\_TP\_BS016 – Revision 7

Effective Date: 01Nov2021

Reference: CS\_WI\_BS005

- o SD, IQR: N + 2

Frequencies and percentages (n and %):

- Percent values should be reported inside parentheses, with one space between the count and the left parenthesis of the percentage. Parentheses should be justified to accept a maximum of 100.0 as a value and padded with blank space if the percent is less than 100.0. An example is given below:

77 (100.0%)

50 ( 64.9%)

0 ( 0.0%)

- Percentages will be reported to one decimal place, except percents <100.0% but >99.9% will be presented as '>99.9%' (e.g., 99.99% is presented as >99.9%); and percents < 0.1% will be presented as '<0.1%' (e.g., 0.08% is presented as <0.1%). Rounding will be applied after the <0.1% and >99.9% rule.

Eg ( <0.1%)

( 6.8%)

(>99.9%)

- Percentages may be reported to 0 decimal places as appropriate (for example, where the denominator is relatively small).
- Where counts are zero, percentages of 0.0% should appear in the output.

Confidence Intervals:

- As a rule confidence intervals are output to one place more than the raw data, and standard deviations and standard errors to two places more than the raw data
- Confidence intervals should be justified so that parentheses displayed on consecutive lines of a table "line up".
- Boundary values of confidence intervals should be separated by a semi-colon.
- Boundary values should be padded as necessary to accept negative values and to allow alignment of the decimal place.
- An example is given below:

(-0.12, -0.10)

( 9.54, 12.91)

P-values:

- P-values should be reported to three decimal places, except values <1.000 but >0.999 will be presented as '>0.999' (e.g., 0.9998 is presented as >0.999); and values <0.001 will be presented as '<0.001' (e.g., 0.0009 is presented as <0.001). Rounding will be applied after the <0.001 and >0.999 rule

Ratios:

Document: BI\_1297-0015\_SAP\_Final\_v1.0  
Author: [REDACTED]

Version Number: Final 1.0  
Version Date: 30Sep2022

Template No: CS\_TP\_BS016 – Revision 7  
Effective Date: 01Nov2021

Reference: CS\_WI\_BS005

---

- Ratios should be reported to one more decimal place than the original data.

**Spacing:**

- There must be a minimum of 1 blank space between columns (preferably 2)

**Denominators:**

- If a different count other than the population count is used for a denominator (within the table) to calculate percentages, there should be a row in the table that identifies that number "n".
- Alternatively, a footnote should be included in each table with percentages to indicate the denominator for percentages.

**Missing values**

- A "0" should be used to indicate a zero frequency.
- A blank will be used to indicate missing data in an end-of-text table or subject listing.

## FIGURE OUTPUT CONVENTIONS

- Figures will be provided in RTF files using the SAS Output Delivery System (ODS) as generated by SAS.
- The image should be clear and of high quality when viewed in the Word document, and when printed.
- In general, boxes around the figures should be used.
- Boxplots will display whiskers extending from P10 to first quartile and from 3rd quartile to P90.

## DATES & TIMES

Depending on data available, dates and times will take the format yyyy-mm-dd; times will take the format hh:mm:ss; combined dates and times will take the format yyyy-mm-ddThh:mm:ss.

## SPELLING FORMAT

English US.

## PRESENTATION OF TREATMENT GROUPS

For outputs, treatment groups will be represented as follows and in that order:

---

Document: BI\_1297-0015\_SAP\_Final\_v1.0  
Author: [REDACTED]

Version Number: Final 1.0  
Version Date: 30Sep2022

Template No: CS\_TP\_BS016 – Revision 7  
Effective Date: 01Nov2021

Reference: CS\_WI\_BS005

Copyright © 2009, 2010, 2012, 2016, 2018, 2019, 2021 [REDACTED]. All Rights Reserved. The contents of this document are confidential and proprietary to [REDACTED] Holdings Inc. and its subsidiaries. Unauthorized use, disclosure or reproduction is strictly prohibited.

Treatment Group
BI 695501 40 mg/0.4 mL
BI 695501 40 mg/0.8 mL

## PRESENTATION OF VISITS

For outputs, visits will be represented as follows and in that order:

Long Name (default)	Short Name
Screening (Day -28 to -2)	Scrn
Day -1	D -1
Day 1	D 1
Day 2	D 2
...	
Day 57	D 57
Day 70	D 70

## PRESENTATION OF NOMINAL TIMES

For outputs, visits will be represented as follows and in that order:

Long Name (default)	Short Name
x hour(s)	x h

## LISTINGS

All listings will be ordered by the following (unless otherwise indicated in the template):

- randomized treatment group (or treatment received if it's a safety output)
- subject ID,
- date including Study day (where applicable),

Document: BI\_1297-0015\_SAP\_Final\_v1.0

Author: [REDACTED]

Version Number:

Final 1.0

Version Date:

30Sep2022

Template No: CS\_TP\_BS016 – Revision 7

Effective Date: 01Nov2021

Reference: CS\_WI\_BS005

---

- For listings where non-randomized subjects are included, these will appear in a category after the randomized treatment groups labelled 'Not Randomized'.

---

Document: BI\_1297-0015\_SAP\_Final\_v1.0  
Author: [REDACTED]

Version Number: Final 1.0  
Version Date: 30Sep2022

Template No: CS\_TP\_BS016 – Revision 7  
Effective Date: 01Nov2021

Reference: CS\_WI\_BS005

## APPENDIX 2. PARTIAL DATE CONVENTIONS

Imputed dates will NOT be presented in the listings.

### ALGORITHM FOR TREATMENT EMERGENCE OF ADVERSE EVENTS:

START DATE	STOP DATE	ACTION
Known	Known Partial Missing	If start date < trial med start date or start date > trial med stop date +70 days, then not TEAE If start date >= trial med start date and start date <= trial med stop date +70 days, then TEAE
Partial, but known components show that it cannot be on or after study med start date	Known Partial Missing	Not TEAE
Partial, could be on or after study med start date	Known	Impute start date as earliest possible date, (i.e. first day of month if day unknown or 1st January if day and month are unknown), except if only day is missing and month and year of start date are the same as for study med start date or if day and month are missing and year of start date is the same as for study med start date. In the later cases, the study med start date will be used for the imputation.  If start date <= stop date, then : If stop date < trial med start date, then not TEAE If start date > trial med end date +70 days, then not TEAE If stop date >= trial med start date and start date <= trial med end date +70 days, then TEAE If start date > stop date, then : Consider the start date as Missing and apply the algorithms for missing start date
	Partial	Impute start date as above. Impute stop date as latest possible date (i.e. last day of month if day unknown or 31 st December if day and month are unknown), if not resulting in a date later than the date of subject's death. In the later case the date of death will be used for imputation.

Document: BI\_1297-0015\_SAP\_Final\_v1.0  
Author: [REDACTED]

Version Number: Final 1.0  
Version Date: 30Sep2022

Template No: CS\_TP\_BS016 – Revision 7  
Effective Date: 01Nov2021

Reference: CS\_WI\_BS005

START DATE	STOP DATE	ACTION
		If start date <= stop date, then : If stop date < trial med start date, then not TEAE If start date > trial med end date +70 days, then not TEAE If stop date >= trial med start date and start date <= trial med end date +70 days, then TEAE If start date > stop date, then : Consider the start and stop dates as Missing and apply the algorithms for missing start date
	Missing	Assumed TEAE
Missing	Known	If stop date < trial med start date, then not TEAE If stop date >= trial med start date, then TEAE
	Partial	Impute stop date as latest possible date (i.e. last day of month if day unknown or 31st December if day and month are unknown), then: If stop date < trial med start date, then not TEAE If stop date >= trial med start date, then TEAE
	Missing	Assumed TEAE

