## 16.1. ADVERSE EVENTS

Adverse Events (AEs) will be coded using Medical Dictionary for Regulatory Activities (MedDRA) central coding dictionary, Version 25.0 or higher. SOCs will be sorted by internationally agreed European Medicines Agency (EMA) SOC order (refer to APPENDIX 3), PTs will be sorted by decreasing frequencies (within system organ class).

In case of worsening in severity, a new entry is created with start date equal to start of worsening.

TEAEs are defined as AEs that started or worsened in severity on or after the single dose of trial medication up to 10 weeks (70 days) post dose.

See APPENDIX 2 for handling of partial dates for AEs. In case it is not possible to define an AE as treatment emergent or not, the AE will be classified by the worst case: i.e. treatment emergent.

An overall summary of number of subjects within each of the categories described in the sub-section below, will be provided as specified in the templates.

Listings will include TEAEs and Non-TEAEs.

Document: BI\_1297-0015\_SAP\_Final\_v1.0  
Author: [REDACTED]

Version Number: Final 1.0  
Version Date: 30Sep2022

Template No: CS\_TP\_BS016 – Revision 7  
Effective Date: 01Nov2021

Reference: CS WI BS005

Copyright © 2009, 2010, 2012, 2016, 2018, 2019, 2021 [REDACTED]. All Rights Reserved. The contents of this document are confidential and proprietary to [REDACTED] Holdings Inc. and its subsidiaries. Unauthorized use, disclosure or reproduction is strictly prohibited.

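### SAP Appendix 2 classes an AE as treatment-emergent although it provably ended before dosing, when its start is known only to the dosing year and its stop only to an earlier month of that year

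*SAP*

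**What the plan says.** SAP 16.1 gives the definition: "TEAEs are defined as AEs that started or worsened in severity on or after the single dose of trial medication", up to 70 days after the dose. It refers to Appendix 2 for partial dates and adds a fallback: "In case it is not possible to define an AE as treatment emergent or not, the AE will be classified by the worst case", that is, treatment-emergent.

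The Appendix 2 table works by the state of the start date, then of the stop date. The rows that matter are these.

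- **Start provably pre-dose** ("Partial, but known components show that it cannot be on or after study med start date"): not a TEAE, whatever the stop date.
- **Start partial and possibly on or after dosing:** the start is set to its earliest possible date. The exception is a start whose month and year, or whose year alone, match dosing: "In the later cases, the study med start date will be used for the imputation".
  - *Stop known.* If the imputed start is later than the stop: "Consider the start date as Missing and apply the algorithms for missing start date".
  - *Stop partial.* "Impute start date as above. Impute stop date as latest possible date". If the imputed start is later than the imputed stop: "Consider the start and stop dates as Missing and apply the algorithms for missing start date".
  - In both cases the test "If stop date < trial med start date, then not TEAE" is made only when start is not later than stop.
- **Start missing, stop partial:** the latest possible stop is compared with dosing, and a pre-dose stop gives not TEAE.
- **Start and stop both missing:** assumed TEAE.

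**The concern.** A start of 2022 and a stop of February 2022 do not disagree with each other. The conflict appears only because the algorithm has moved the start to the dosing date. The partial/partial branch treats this self-made conflict as a reason to throw away the stop date, the one item that settles the status.

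The classification then depends on whether the day of the stop date was written down, and an event with a known start year is classed less accurately than one with no start date. For this pattern the error runs in one direction: it adds TEAEs that are not treatment-emergent. At stake is the accuracy of the TEAE counts and the SAP's consistency with its own worst-case rule. No PK result is involved.

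**Working it through.** No stated figure has to be reproduced; the check is of decision logic.

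**Why the pre-dose test cannot work in this branch.** Let D be the dosing date, S the imputed start and E the imputed stop. In this row S equals D if the start's month and year, or its year alone, match dosing; otherwise it is the first day of a later month or year. So S ≥ D always. The test needs S ≤ E and E < D together, which would mean S < D. That is impossible, so the line can never be reached. Whenever E < D, S > E follows, both dates become missing, and the event is assumed a TEAE.

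**Example, dosing 20 March 2022** (dates chosen for illustration):

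| Recorded start | Recorded stop | Path | Result |
|---|---|---|---|
| 2022 | Feb 2022 | S = 20 Mar, E = 28 Feb; conflict; both missing | TEAE |
| 2022 | 25 Feb 2022 | S = 20 Mar; conflict; start missing; 25 Feb < 20 Mar | not TEAE |
| missing | Feb 2022 | E = 28 Feb < 20 Mar | not TEAE |
| Feb 2022 | Feb 2022 | start provably pre-dose | not TEAE |
| Apr 2022 | Feb 2022 | S = 1 Apr, E = 28 Feb; conflict; both missing | TEAE |

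The first three rows are consistent with one and the same event. The last is a contradictory record, a different matter. SAP Appendix 2 also gives rules for medications: a medication with start 2022 and stop February 2022 has its stop set to 28 February and is classed as prior.

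**Enumeration.** The table was coded literally for every dosing date in 2022 (an assumed year), crossed with every month-year and year-only start and stop in 2021 to 2023.

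- Patterns in the partial/partial branch with E < D: 134,106. All were classed TEAE; the branch's own pre-dose test was reached 0 times.
- Of these, patterns in which the recorded dates are compatible: 2,017, all with a year-only start in the dosing year. By hand, each dosing day contributes the number of earlier months in its year, so for February to December: 28×1 + 31×2 + 30×3 + 31×4 + 30×5 + 31×6 + 31×7 + 30×8 + 31×9 + 30×10 + 31×11 = 2,017.
- Contradictory patterns, with the start period wholly after the stop period: 134,106 − 2,017 = 132,089.

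**Effect of discarding only the start date.** All 134,106 patterns become not TEAE, and none of the other 157,341 patterns in the branch changes class (99,707 stay TEAE, 57,634 stay not TEAE). Restricted to compatible dates, the change moves only the 2,017.

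These are counts of date patterns, not of expected events.

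**Room for the case in this trial.** AEs are recorded from consent (Protocol 5.2.6.2.1) and screening lasts at most 28 days (Protocol 3.1). Assume that consent falls inside that window. The stop month must then end on or after Day -28, so the dosing day of the month must be 28 or less and the stop must be in the preceding month: 11 months × 28 days = 308 of the 2,017 patterns (308/2,017 = 15%).

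**The case against.** **It hardly ever happens.** Two incomplete dates are needed. Protocol 8.3.1 lists the AE onset date as mandatory, though it does not say that the date must be complete. Conditions that exist before inclusion are baseline conditions (Protocol 5.2.6.1.1). In the example, Day -28 is 20 February, so under the consent assumption the event must have started and stopped between 20 and 28 February, and a query could settle it. This stands, and it sets the size of the point.

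**Nothing hangs on it.** Safety analysis is descriptive (Protocol 7.2.5), the primary endpoints are PK, and the rule is the same in both arms. Listings show TEAEs and other AEs without imputed dates, so the recorded partial dates stay visible. This also stands.

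**It is deliberate caution.** For contradictory records this is a fair defence: with start April and stop February one date is wrong, the stop proves nothing, and defaulting to TEAE fits SAP 16.1. For compatible dates it fails, because the status can be determined and the branch itself contains a test meant to exclude pre-dose stops.

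**The row for provably pre-dose starts might catch it,** if the stop month counts as one of the known components. But that row describes the start date and applies to every state of the stop date. If stop dates were used there, the known-stop branch would not need its own route to not TEAE.

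**The obvious edit has a price.** Discarding only the start date in every conflict would also turn contradictory records, such as start April with stop February, into not TEAE, although the recorded onset is after dosing. This stands and shapes the fix.

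**Conclusion.** The rule is wrong as written for one pattern of genuine dates: a start known only to the dosing year and a stop known only to an earlier month of that year. Such an event is classed as a TEAE every time, against the SAP 16.1 definition and against the neighbouring rows.

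Two stronger readings are tempting but not supported. A reader might infer that any AE with a pre-dose stop month is counted as treatment-emergent. It is not: known starts are judged on the start, provably pre-dose partial starts are excluded by their own row, and missing starts are judged on the stop. A reader might also count all 134,106 patterns as errors; 132,089 of them are contradictory records, for which the default is defensible.

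The effect is small. With about 100 subjects per arm, one such event changes an incidence by at most 1/100, or 1 percentage point, in a descriptive table. The conclusion rests on a literal reading of the table. Dates with the year unknown, or with only the month missing, are not covered by Appendix 2 and were not assessed. This is a tidy-up, worth making because it is cheap.

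**What to change.** In the partial-start/partial-stop branch, split the conflict rule in two.

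1. **Compatible dates** (the recorded start period does not lie wholly after the recorded stop period): set only the start date to missing, keep the latest possible stop, and apply the row for missing start with partial stop.
2. **Contradictory dates** (the recorded start period lies after the stop period): query the record, and keep the TEAE default if the query does not resolve it.

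The simpler alternative is to reword the conflict rule so that it discards the start date alone, as the known-stop branch does. That is a one-phrase edit. If it is chosen, the SAP should state its downside: contradictory records with a pre-dose stop would also become not TEAE.

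Either version costs a short text change in Appendix 2 and its program, with an entry in the SAP's modification history; the first also needs one extra date comparison. Data collection, design and the PK analysis are unaffected. A search for records with this date pattern before unblinding would show whether any event changes class; if none does, the edit leaves the tables as they are.

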### ALGORITHM FOR PRIOR / CONCOMITANT MEDICATIONS:

Partial date to be imputed as:

Start date	Earliest possible date	first day of month if day unknown or 1 st January if day and month are unknown
Stop date	Latest possible date	last day of month if day unknown or 31 st December if day and month are unknown

General rules:

If stop date < trial med start date, assign as prior

If start date >= trial med start date and start date <= end of trial date on Day 70, assign as concomitant

Document: BI\_1297-0015\_SAP\_Final\_v1.0

Author:

Version Number:

Final 1.0

Version Date:

30Sep2022

Template No: CS\_TP\_BS016 – Revision 7

Effective Date: 01Nov2021

Reference: CS\_WI\_BS005

**If Missing stop date : (Rules 2)**

If stop date is missing could never be assumed a prior medication

If start date <= end of trial date on Day 70, assign as concomitant

**If Missing Start date : (Rules 3)**

If stop date < trial med start date, assign as prior

If stop date >= trial med start date, assign as concomitant

START DATE	STOP DATE	ACTION
Known	Known	General rules
	Partial	General rules
	Missing	Rules 2
Partial	Known	General rules
	Partial	General rules
	Missing	Rules 2
Missing	Known	Rules 3
	Partial	Rules 3
	Missing	Assign as concomitant

---

**APPENDIX 3. EMA SOC ORDER FOR PRESENTATION OF THE AE IN THE TABLES.****Order System Organ Class**

- 0 Uncoded
- 1 Infections and infestations
- 2 Neoplasms benign, malignant and unspecified (incl cysts and polyps)
- 3 Blood and lymphatic system disorders
- 4 Immune system disorders
- 5 Endocrine disorders
- 6 Metabolism and nutrition disorders
- 7 Psychiatric disorders
- 8 Nervous system disorders
- 9 Eye disorders
- 10 Ear and labyrinth disorders
- 11 Cardiac disorders
- 12 Vascular disorders
- 13 Respiratory, thoracic and mediastinal disorders
- 14 Gastrointestinal disorders
- 15 Hepatobiliary disorders
- 16 Skin and subcutaneous tissue disorders
- 17 Musculoskeletal and connective tissue disorders
- 18 Renal and urinary disorders
- 19 Pregnancy, puerperium and perinatal conditions
- 20 Reproductive system and breast disorders
- 21 Congenital, familial and genetic disorders
- 22 General disorders and administration site conditions
- 23 Investigations
- 24 Injury, poisoning and procedural complications
- 25 Surgical and medical procedures
- 26 Social circumstances
- 27 Product issues

---

## APPENDIX 4. BIcMQs

BIcMQs identification is based on a separate external excel file named:

- BIcMQ\_25.0\_Administration\_site\_reactions

MedDRA version 25.0 or higher will be used.

---

Document: BI\_1297-0015\_SAP\_Final\_v1.0  
Author: [REDACTED]

Version Number: Final 1.0  
Version Date: 30Sep2022

Template No: CS\_TP\_BS016 – Revision 7  
Effective Date: 01Nov2021

Reference: CS\_WI\_BS005
